4.3 Imaging

No extra scans will be performed in the trial. The diagnostic magnetic resonance scan (MR), the planning computed tomography (CT) and the cone-beam CT scans used for set-up of the patient for treatment will be transferred to a research computer and used for training of an artificial intelligence (AI) software algorithm that automatically can outline the target area, the esophagus and stomach and compute an optimized radiotherapy plan. The computer is located behind the hospital firewall and meets all requirements for handling person-sensitive data.

4.4 Supplemental treatment

Analgesic drugs, corticosteroids, antacids and other supportive medicine during and after treatment are prescribed at the discretion of the referring physician. The use of these medications is reported in the electronic case report form (e-CRF)

4.5 Systemic therapy

Antineoplastic systemic therapy can be paused before, during and after radiation at the discretion of the physician, depending on the interaction with radiotherapy. The use of antineoplastic systemic therapy is reported in the e-CRF.

5 Participants

ESO-SPARE - Esophagus-sparring radiotherapy: 200 patients will be included in the study.

GLUC-DIAB - Glucocorticoid-induced diabetes: 150 patients will be included in the study.

5.1 Inclusion criteria

ESO-SPARE

- Histology or cytology proven cancer
- Referred for palliative radiotherapy of the **cervical or thoracic vertebra** for
 - epidural ingrowth
 - metastatic spinal cord compression
 - metastatic spinal nerve root compression
 - post-operative radiotherapy after decompressive surgery for spinal cord or nerve root compression
- Ability to understand and the willingness to sign a written informed consent document
- Ability to complete follow-up questionnaires, assessed by local investigator
- Referred for the following dose prescriptions 5 Gy x 5, 3 Gy x 10, 10 Gy x 1, 8 Gy x 1.
- ≥ 18 years old.

GLUC-DIAB

- Histology or cytology proven cancer
- Referred for palliative radiotherapy of **all spinal** levels for

- epidural ingrowth
- metastatic spinal cord compression
- metastatic spinal nerve root compression
- post-operative radiotherapy after decompressive surgery for spinal cord or nerve root compression
- Ability to understand and the willingness to sign a written informed consent document
- Ability to complete follow-up questionnaires, assessed by local investigator
- Referred for the following dose prescriptions 5 Gy x 5, 3 Gy x 10, 10 Gy x 1, 8 Gy x 1.
- ≥ 18 years old.
- No history of diabetes and $\text{HbA}_{1\text{C}} < 48$ mmol/mol, see **Figure 4**.

5.2 Exclusion criteria

- Age < 18 years
- Referred for > 10 fractions
- Exclusion criteria, $\text{HbA}_{1\text{C}}$ validation and glucose monitoring (GLUC-DIAB): history of diabetes, $\text{HbA}_{1\text{C}} > 48$ mmol/mol.

5.3 Enrolment

ESO-SPARE is a regional multi-center study recruiting patients referred for palliative radiotherapy of radiotherapy of the vertebra at Rigshospitalet or Herlev Hospital. The treatment is given sub-acute and patients are often referred, planned and receiving their first treatment fraction within the same day. This means that the participants time for considering inclusion in the trial is short.

Potential participants (subjects) will be informed about the trial when they meet for treatment planning in the department's radiotherapy section. A member of the project team will provide verbal and written information on the trial and the subject will be provided with full and adequate information about the objectives, the study outlines and possible risks and benefits of participating in the trial. The information will be given under private conditions, and the subject will be encouraged to discuss participation with a relative or friend. If no relative or friend is present, the

subject is encouraged to call them on telephone and the project team member will give information to the friend or relative as well. The subjects have the right to ask questions about the study and should be given time, to make the decision to participate in the study or not. Because of the subacute treatment course only short time (1 hour) can be given for consideration.

The subjects should be clearly informed that the data collected in the study will not identify any subject taking part in the study, following the Data Protection Act and the General Data Protection Regulation (GDPR) (EU) 2016/679.

The subjects should be informed that it is voluntary to participate and that they can withdraw from the study at any time without giving any reason. The subjects should further be informed that a decision not to participate in the study or to withdraw will not be questioned or effect their future medical care or treatment at the clinic.

Written Informed Consent must be obtained from all participating subjects before enrolment in the study. The Informed Consent form should also be signed, at the same occasion, by the investigator who gave the written and verbal information. No trial related procedures can take place unless a written informed consent is obtained.

The subjects will consent to participation in the study; regulatory authorities to gain full access to hospital records, to control the data collected in the study; recording, collecting and processing of data and storing data in a database. Contact information for the physician responsible of the study will be provided. If the subject chooses not to participate in the study, he or she will continue the standard treatment.

Patients may choose to participate in ESO-SPARE (esophagus sparing radiotherapy) or GLUC-DIAB (HbA_{1c} validation and glucose monitoring) only.

Participants will not be informed of randomization outcome.

Patients randomized to esophagus sparing radiotherapy needing reirradiation (**other target that primarily prescribed**) during the 9 weeks of FU, will receive esophagus sparing radiotherapy for the second target.

Participants will not receive remuneration.

5.4 Withdrawal from the study

A patient may be withdrawn from the study if any of the following events occur:

- If, in the opinion of the investigator, withdrawal is necessary for medical or technical reasons
- Major protocol violation
- Informed consent withdrawal

In case of a withdrawal before first treatment day, another patient will be enrolled (with a new patient number). The withdrawn patient will be accounted for in the statistical analysis. The reason for withdrawal should be clearly described. Relevant data should be obtained when possible, and all relevant assessments should be completed, preferably according to the schedule for the final assessment. The eCRF should be completed.

5.5 End of study

Participants are active in the study until 9 weeks after radiotherapy or death whichever comes first. The participants are passively followed with registration of further courses of radiotherapy and OS.

6 Radiotherapy planning

6.1 Simulation

A CT scan with the patient immobilized in the treatment position is required for delineation. A CT slice thickness of minimum 2 mm is recommended. A variety of immobilization devices may be used. The use of intravenous contrast enhancement is optional.

An MRI of the spine with or without contrast enhancement is usually conducted by the radiology department as a part of the diagnostic process prior to referral. The MRI images available are used as an aid in treatment planning. A MRI is optional, for patients with contraindications for MRI.

The FreeStyle Libre censor will be applied outside the radiation field after the planning CT is performed.

6.2 Dose prescription

See Table 3 for dose prescriptions included in this study. The treatment is prescribed prior to inclusion at the discretion of the referring physician.

Fractionation (Dosis x Fraction)	Total Physical Dosis (Gy)	Maximum delivery time (days)
5 Gy x 5	25	14
3 Gy x 10	30	21
10 Gy x 1	10	1
8 Gy x 1	8	1

Table 3. Fractionation schedules included in ESO-SPARE

6.3 Target and organs at risk

Delineation of the CTV is conducted in accordance to local guidelines.¹²

- CTV includes the tumor affected vertebral body and adjacent soft tumor tissue (If any). CTV will often include the spinal canal, pediculus and arcus posterior. Processus transversi and spinosus will not be included in the CTV unless there is tumor infiltration here. Cranial/caudal delineation is limited by the upper and lower edge of the affected vertebrae. If the target area involves more than one vertebra, these may be included in the same CTV if they are separated by no more than 2 healthy vertebrae. If they are separated by 3 or more healthy vertebrae, two separate CTVs must be defined.
- The planning target volume (PTV) is computed by adding a 5 mm margin around the CTV.
- Esophagus and stomach are delineated for all patients
- Any other OAR is only to be delineated if the organ is expected to receive a relevant radiation dose (at the discretion of the treating physician).
- Local guidelines for dose constrains in palliative treatment will be followed.²²

6.4 Esophagus sparing radiotherapy vs. standard treatment

For the patients in the standard arm, a standard radiotherapy plan computed using VMAT technique aiming at covering the PTV with at least 90 % of the prescribed dose and not taking the dose to the esophagus and/or stomach into account.

For the patients in the interventional arm, a plan using VMAT technique is computed aiming at keeping the maximum dose to the esophagus and/or stomach as described in Table 4. Even if it means compromising the dose to the PTV and CTV.

Patients randomized to esophagus sparing radiotherapy needing reirradiation (**other target that primarily prescribed**) during the 9 weeks of FU, will receive esophagus sparing radiotherapy for the second target.

	Maximum Physical Esophageal Dose ($D_{0,027\text{cm}^3}$) (Gy)		Max. Esophageal Dose in EQD2 ($D_{0,027\text{cm}^3}$) (Gy), $\alpha/\beta = 3$ Gy	
Fractionation (Dosis (Gy) x Fraction)	Standard arm	Esophagus sparing arm	Standard arm	Esophagus sparing arm
5 Gy x 5	25	8,5	40	8
3 Gy x 10	30	10	36	8
10 Gy x 1	10	5	26	8
8 Gy x 1	8	5	17,6	8

Table 4. Maximum esophageal dose. Standard arm vs. esophagus sparing arm.

7 HbA_{1c} and Flash glucose monitoring

HbA_{1c} will be measured at baseline, which is standard procedure in one of the participating centers.

²³ In order to obtain ambulatory glucose profiles for retrospective glucose data analysis we will use a blinded professional sensor-based Flash glucose monitoring system (FreeStyle Libre Pro™; Abbott Diabetes Care, Witney, UK).^{19,20} The sensor is worn on the upper arm for 14 days. The sensor is factory calibrated which means that, after activating the sensor at baseline, no further intervention during the 14-day wear is required. As the sensor is blinded, data are not visible to participants or investigators during sensor wear. The sensor automatically captures and stores glucose data every 15 min (96 glucose readings/day). After 14 days the sensor is dismantled, and glucose data are wirelessly transferred to the pro-reader. Summary glucose reports are generated using the system software. Patients in our study will be followed for 28 days after start of radiotherapy treatment requiring one sensor change. This will include time without glucocorticoid treatment.

The patients participating in this part of the study will not be subject to standard glucose measurements; instead they will be thoroughly instructed to contact the PI if symptoms of hyperglycaemia should occur.

Patients not participating in Flash glucose measurements will follow local guidelines for glucose measurements. Current standard glucose measurements (for patients with no prior history of diabetes) in the two participating centers are summarized in Table 5 and 6.

Baseline HbA _{1c}	Frequency of glucose measurements
≤39 mmol/mol	No measurements
40–47 mmol/mol	Twice weekly
≥48 mmol/mol	Diagnostic for diabetes, glucose measurements minimum 4 times daily at the discretion of local diabetes team

Table 5 Standard glucose measurements Herlev Hospital. Frequency of glucose measurements is based on baseline HbA_{1c}. Patients presenting with 2 glucose values above 11 mmol/L are referred to the local diabetes team for further treatment planning. It is advised that severe hyperglycemia (BS>15-20 mmol/L) is avoided²³.

Plasma glucose	Frequency of glucose measurements
>15 mmol/L	Once daily
>20 mmol/L	A physician is consulted for further planning
>25 mmol/L	Insulin treatment should be initiated

Table 6 Standard glucose measurements Rigshospitalet. Glucose is measured twice weekly in all patients¹⁷.

8 Safety assessment

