1.3 Glucocorticoid-induced diabetes

High dose glucocorticoid is used in MSCC to decrease inflammation and edema in the affected vertebra and neural tissue. In our clinic, patients are started on high-dose glucocorticoids (150 mg Prednisolone daily) when MCSS is suspected. During radiotherapy the dose is reduced to 75 mg daily. A minimum 5 days of treatment are mandatory, even for patients treated with single fraction. High-dose glucocorticoid treatment may be discontinued after 5 days or after end of radiotherapy treatment, whichever comes first. Depending on symptoms and duration of prior glucocorticoid treatment some patients may benefit from a gradual decrease. ^{12,13}

It is well established that glucocorticoid treatment can induce new-onset hyperglycemia and even glucocorticoid-induced diabetes mellitus (GIDM) in patients without a history of diabetes mellitus (DM) ¹⁴. Hyperglycemia has been associated with complications such as longer hospital stays, delayed wound healing, increased infections and higher mortality rates. ¹⁴

As of now there are only two studies describing glucocorticoid-induced diabetes in patients receiving treatment for MSCC. ^{15,16} Schultz et al performed a prospective study including 131 patients receiving high-dose glucocorticoids for MSCC. The patients were monitored with 1-3 finger prick glucose measurements for 12 days after treatment start. 43% of the patients presented plasma glucose values diagnostic of diabetes and 12% were treated with insulin¹⁵. A HbA_{1c}-value <39 mmol/mol was associated with a negative predictive value of 96% for not developing diabetes needing treatment with insulin.¹⁵

While insulin-treated diabetes was mainly diagnosed in the first week after treatment start, the incidence of non-insulin treated diabetes was rising through-out the study period¹⁵. There are no data describing glucose levels beyond the study period of 12 days.

[figure not shown]

Figure 3 Time course of development of diabetes¹⁵

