2 ESO-SPARE

We propose a phase III trial – ESO-SPARE, with randomization to esophagus sparing radiotherapy or standard of care radiotherapy for patients treated for MSCC in the thoracic and cervical spine. The primary aim of ESO-SPARE is to examine if advanced radiotherapy planning and delivery of radiotherapy with sparing of the esophagus can decrease patient reported esophageal toxicity.

Concurrently we want to conduct a observational study of glucocorticoid diabetes in patients with metastatic spinal cord compression (the GLUC-DIAB study). In this study we wish to characterize the spontaneous course of blood-glucose level during and after high-dose glucocorticoid treatment and validate the HbA_{1c} cut-off used in the clinic to identify patients in low risk of developing glucocorticoid-induced insulin-dependent DM.

We have the following research questions:

- Can esophagus sparing radiotherapy significantly decrease patient reported esophageal toxicity in patients with metastatic spinal cord compression without compromising their ambulatory function?
- Will esophagus sparing radiotherapy increase other toxicities compared to standard radiotherapy?
- What is the spontaneous course of blood-glucose level during and after high-dose glucocorticoid treatment for patients with MSCC?
- What is the incidence of glucocorticoid-induced diabetes in patients with MSCC?
- How many of the patients that develop glucocorticoid-induced diabetes, have normalized their plasma-glucose values on day 28 after start of glucocorticoid treatment?
- Can HbA1c be used as a negative predictive value for not developing insulin demanding diabetes?
- What is the incidence of hospital admissions due to new-onset diabetes?

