The QoL questionnaires EuroQol EQ-5D-5L Index and EORTC QoL C30, which are standardized and validated instruments, will be used to measure participants' quality of life (QoL) during follow up.

The EQ-5D index is a relatively simple five-item questionnaire (measuring mobility, self-care, usual activities, pain/discomfort, and anxiety/depression). It produces a composite score between 0 and 1 (multiplied by 100 to yield a result between 0-100).

The EORTC QoL C30 is more detailed and will be used to calculate measures for physical function.

See appendix B and D.

4.1 HbA_{1c} and Flash glucose monitoring.

HbA_{1c} will be measured at baseline. The blinded Flash glucose monitoring system FreeStyle Libre Pro (FreeStyle Libre Pro™; Abbott Diabetes Care, Witney, UK) will be used to obtain continuous glucose measurements for 28 days from baseline.^{19,20} The sensor must be changed after 14 days. This can be done in relation to another hospital appointment or by the patient at home with video assistance if necessary.

Data will only be extracted after the second sensor is dismantled. For quality assurance data will be extracted from the first sensor in the first 5 participants.

If the patients experience symptoms of hyperglycemia or hospitalized, glucose measurements will be at the discretion of the treating physician. See section 4.3 toxicity assessment.

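### GLUC-DIAB counts its glucose endpoints from conflicting time origins, and the sensor can start after steroid exposure has begun

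*Protocol*

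**What the plan says.** The research question in Protocol section 2 asks how many patients who develop steroid-induced diabetes "have normalized their plasma-glucose values on day 28 after start of glucocorticoid treatment". The matching endpoint in section 2.3 also uses day 28, but from the start of an unspecified treatment. Section 4.1 plans "continuous glucose measurements for 28 days from baseline", with baseline taken at the radiotherapy planning visit (section 4). Section 7 says: "Patients in our study will be followed for 28 days after start of radiotherapy treatment requiring one sensor change". Table 2 also counts from radiotherapy.

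On exposure, section 1.3 says that "patients are started on high-dose glucocorticoids (150 mg Prednisolone daily) when MCSS is suspected", then "During radiotherapy the dose is reduced to 75 mg daily", and adds: "A minimum 5 days of treatment are mandatory, even for patients treated with single fraction". On the device, section 6.1 says: "The FreeStyle Libre censor will be applied outside the radiation field after the planning CT is performed". Section 5.1 admits patients referred for "post-operative radiotherapy after decompressive surgery for spinal cord or nerve root compression", and no criterion limits earlier steroid use.

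The HbA1c limit for entry is worded in three ways: 48 mmol/mol or more is not included (section 3.5), below 48 is required (section 5.1), and above 48 is excluded (section 5.2). The SAP lists no glucose endpoint and no glucose analysis.

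**The concern.** The exposure of interest starts with the first steroid dose, but observation starts at planning. If days pass in between, two things follow. First, a status read 28 days after baseline or radiotherapy start falls on a later steroid day, and that day differs between patients, so the normalisation count mixes different times since steroids began and stopped. Second, the course during treatment and the incidence of steroid-induced diabetes can lack the earliest days, all of them at the higher dose. Section 1.3 reports that insulin-treated cases in the earlier cohort appeared mostly in week one, so these days are informative. Section 9.1 also expects fewer cases than in that cohort because steroid doses have come down. A late start of observation could push the observed rate the same way, and the two explanations could not be separated unless the lag is known.

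**Working it through.** **The plan's own figures.** 28 days / 14 days per sensor = 2 sensors, so one change. 24 x 60 / 15 = 96 readings a day. Both agree with section 7.

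**Inputs.** Steroid start at suspicion, 150 mg then 75 mg, minimum 5 days (section 1.3). Sensor after the planning CT (section 6.1), worn for 28 days. Let k be the days from first steroid dose to sensor start. The documents give no value for k. Section 5.3 says referral, planning and first fraction often share a day, but that does not cover suspicion to sensor. I take k = 0 to 7 as an assumption.

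**Shift of the time axis.** Counting the first day on each scale as day 1:

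- the trace covers steroid days k + 1 to k + 28;
- steroid day 28 is sensor day 28 - k;
- sensor day 28 is steroid day 28 + k;
- share of the first steroid week off the trace = k / 7.

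| k | Steroid days on the trace | Sensor day of steroid day 28 | Steroid day of sensor day 28 | Week 1 unobserved |
|---|---|---|---|---|
| 0 | 1-28 | 28 | 28 | 0% |
| 1 | 2-29 | 27 | 29 | 14% |
| 2 | 3-30 | 26 | 30 | 29% |
| 3 | 4-31 | 25 | 31 | 43% |
| 7 | 8-35 | 21 | 35 | 100% |

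Steroid day 28 stays on the trace throughout, so it can be recovered once the first-dose date is known. Table 2 registers steroids at baseline but does not name a start date.

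**Exposure before the sensor.** For an illustrative 5-day course at 150 mg before sensor start and 75 mg after, the share of total dose given before the sensor is 150k / [150k + 75(5 - k)]: 0/375 = 0% for k = 0, 150/450 = 33% for k = 1, 300/525 = 57% for k = 2 and 450/600 = 75% for k = 3.

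**Time since last dose.** With a course of D days, steroid day 28 lies 28 - D days after the last dose: 23 days for D = 5, and 14 days for an assumed D = 14. One common origin therefore still leaves variation in time off steroid. Section 1.3 foresees a gradual decrease in some patients.

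**The case against.** Part of any gap cannot be avoided, because section 5.3 allows no trial procedure before consent at the planning visit. The lag is undocumented, so a flat statement that the sensor misses the first days would go too far; it can miss them. Day 28 is recoverable by realignment. All of this stands, and it limits the point to wording, recorded dates and analysis.

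Three stronger readings are tempting, and the documents do not support them.

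*That early cases are lost.* Spreading the earlier cohort's 12% insulin-treated cases evenly over week one would give 12 x (1 - 1/7) = 10.3% seen with a lag of 1 day and 12 x (1 - 3/7) = 6.9% with 3 days. That requires every early case to be excluded or to resolve before the sensor. Yet sections 2.4 and 2.6 define the outcome by plasma glucose during steroid treatment, not by sensor wear. Table 2 registers antidiabetic medication from baseline, and steroids continue into radiotherapy, so an early rise can still show on the trace. The 12% also comes from a cohort on 300 mg for 10 days (section 9.1).

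*That the HbA1c limit removes many steroid-caused cases.* A few days of steroid should move HbA1c little. Assume it averages glucose over 120 days, with 3 days weighted 3/120 = 2.5% (uniform) to 1 - (1 - 3/120)^2 = 4.9% (recent days weighted more). Assume also about 6.9 mmol/mol per mmol/L and a glucose rise of 5 to 10 mmol/L. The shift is then 0.025 x 5 x 6.9 = 0.9 to 0.049 x 10 x 6.9 = 3.4 mmol/mol. Only patients already near 48 would cross. Weeks of earlier steroid, which the criteria permit, could matter more, but the documents do not say how common that is.

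*That HbA1c exclusions flatter the cut-off.* The quantity under validation is the negative predictive value below 39 mmol/mol. Patients at 48 or more lie above the cut-off, so removing them cannot change it. If they were insulin cases, their removal would lower apparent sensitivity.

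Nor does the point justify a changed entry rule. One HbA1c taken after steroids began cannot separate undiagnosed earlier diabetes from steroid-induced diabetes, and baseline HbA1c is standard in only one centre (section 7). Admitting such patients to blinded monitoring is a clinical matter.

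**Conclusion.** The inconsistency of time origins is plain in the text, and nothing in the SAP resolves it. Any steroid taken between suspicion and radiotherapy is at the higher dose, and the sensor cannot see what precedes it. As written, day-28 normalisation may be read k days late, differently in each patient. With an assumed lag of 1 to 3 days, 14 to 43% of the first steroid week is off the trace. These are shares of time, not of cases, and they fall to zero if the lag is zero. The endpoints are secondary for the trial but central to GLUC-DIAB, so the change should be made.

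A smaller gap remains at entry. The documents set no date at which a history of diabetes is judged and do not say how to handle diabetes first recorded between the first steroid dose and inclusion. The size of this is unknown. It calls for transparent reporting, not for different eligibility.

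**What to change.** - Make the first steroid dose the time origin for every GLUC-DIAB endpoint, and align Protocol sections 2, 2.3, 4.1 and 7 and Table 2 with it.
- Record the dates of first and last steroid dose, HbA1c sample and sensor start. Report the distribution of the lag.
- Read normalisation at steroid day 28 on the existing trace (sensor day 28 minus the lag), and also report it by days since last steroid dose.
- From the hospital records already accessed under section 4, take insulin starts and plasma glucose between first steroid dose and sensor start. Report incidence with and without these events. Table 5 has no routine measurements at HbA1c of 39 or below in one centre, while Table 6 has twice-weekly measurements for all in the other, so pre-sensor detection depends on centre and HbA1c.
- Leave eligibility as it is. List patients not included because of HbA1c of 48 or more, or because of diabetes first recorded after steroid start, with their prior steroid days. Reconcile the HbA1c limits in sections 3.5, 5.1 and 5.2.

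The cost is protocol wording and a few chart items per patient, feasible even after accrual. Pre-sensor glucose will remain sparse and uneven.
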